5.4 Adherence Assessment

Subject adherence is defined by subjects completing at least 6 out of 7 days of their daily symptom diary during the last week of the study period and taking amitriptyline

or omeprazole at least 6 out of 7 days during that week. Adherence will be assessed when subjects return their symptom diaries at their follow-up visit. For subjects who return incomplete symptom diaries, average daily symptom severity for the days completed will be calculated. If there is insufficient data to make this calculation, we will assume that symptoms are unchanged from baseline.

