- Amitriptyline: The most common side effects are dry mouth, sleepiness, and constipation. Less common side effects include dizziness, fatigue, headache, agitation, tremor, blurred vision, nausea, insomnia, and sexual dysfunction. Rare side effects include an allergic reaction, changes in heart conduction causing slowing or speeding up of the heart rate, serotonin syndrome, and suicidal ideation. We are prescribing low doses of this medication and have excluded those most vulnerable to adverse effects and so do not anticipate any serious adverse events. If a study subject calls with concerns about side effects, they will be directed to speak with a physician on the study team to assess their symptoms and determine whether any dose modification or further evaluation is needed. If it is deemed that the subject should stop the medication, they will be instructed in how to do so. If it is determined that they need further medical evaluation, they will be instructed what to do.
- Omeprazole: The most common side effects are headaches, abdominal pain, diarrhea, and nausea. Less common side effects include skin rash, constipation, dizziness, and back pain. Rarely someone may develop a hypersensitivity reaction, acute interstitial nephritis, lupus, or an enteric infection. Long-term use may increase the risk of

fractures, vitamin B12 deficiency, or low magnesium levels. Despite these risks, omeprazole is generally well-tolerated and available over-the-counter. If a study subject calls with concerns about side effects, they will be directed to speak with a physician on the study team to assess their symptoms and determine whether any dose modification or further evaluation is needed. If it is deemed that the subject should stop the medication, they will be instructed in how to do so. If it is determined that they need further medical evaluation, they will be instructed what to do.

- Severe GERD symptoms: It is possible that subjects may experience a flare in their GERD symptoms during the study. If a subject calls with severe GERD symptoms, he or she will be directed to speak with a study physician to discuss their symptoms and determine the best course of action. In some cases as needed antacids may be recommended for refractory symptoms. If this recommendation does not suffice, the subject may need to initiate additional medication and possibly be removed from the study.

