8. INTERVENTION DISCONTINUATION

Subjects who decline to participate in study procedures (e.g., completion of study questionnaires, physiologic monitoring, and/or video recording) will be terminated from the study without further follow-up. Any subjects who are disruptive or felt to pose a threat to study staff will also be terminated without follow-up. If a subject experiences an adverse reaction to amitriptyline or omeprazole and decides to stop taking the medication, or if a study physician deems it in the subject's best interest to stop the medication, the subject will continue to be followed for the duration of their initially planned participation (out to 8 weeks), unless the subject declines to participate further.

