9. STATISTICAL CONSIDERATIONS

9.1 General Design Issues

Design: This is a single-blinded randomized controlled trial in which subjects will be randomized in a 1:1 fashion to receive either an expanded or standard visit with a healthcare provider about their GERD symptoms and then treated with amitriptyline or omeprazole for 8 weeks to determine whether an expanded visit can augment the effects of a medication compared to a standard visit.

Primary hypotheses:

1. Subjects who receive an expanded visit will have a greater improvement in their GERD symptoms after 8 weeks of treatment with amitriptyline or omeprazole compared to subjects who receive a standard visit.

Secondary hypothesis:

1. Patient-provider dyads in expanded visits will have a greater percentage of the total visit time spent in physiologic concordance (measured by either GSR or HRV) compared patient-provider dyads in standard visits.
2. Percentage of visit time with physiologic concordance (in GSR or HRV) will be correlated with GERD symptom improvement.
3. Subjects who experience physiologic changes similar to those elicited by mind-body techniques (i.e., decreased GSR and increased high frequency HRV) over the course of their visit (first several minutes compared to the last several minutes of the visit) will demonstrate greater improvements in GERD symptom severity than subjects who do not.

4. Healthcare providers in expanded visits will demonstrate more patient-centered non-verbal behaviors (e.g., smiles and gazes) and global impression (e.g., engaged, friendly, relaxed) compared to providers in standard visits as rated by blinded reviews of thin slices of video excerpts.
5. Patient and provider smiling at the end of study visits will be significantly associated with GERD symptom improvement 8 weeks later.

Primary outcome:

1. Change in the average daily GERD symptom severity score from baseline to the last week of the study in the expanded vs. standard group. GERD symptom severity is based on the sum of scores assessing the severity of daytime heartburn, nighttime heartburn, and acid reflux each on a 0-4 point scale (none, mild, moderate, severe, very severe; higher scores signify worse symptoms).

Secondary outcomes:

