9.3 Definition of Populations

For analyses including the intervention group type, we will analyze our data according to which visit intervention subjects received (standard or expanded). We do not anticipate any discrepancies between what subjects were assigned to receive by randomization and what they actually received. Study visit type will be guided by a written script that the providers will follow during the visit. The actual intervention received will also be verified by reviewing study video recordings.

The intent to treat analysis will include all randomized subjects who received a study visit intervention. The per protocol analysis will include all individuals who received a study visit intervention and completed the follow-up questionnaires at 8

weeks.

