9.5.1 Primary Outcome

1. Change in the average daily GERD symptom severity score from baseline to the last week of the study in the expanded vs. standard group. GERD symptom severity is based on the sum of scores assessing the severity of daytime heartburn, nighttime heartburn, and acid reflux each on a 0-4 point scale (none, mild, moderate, severe, very severe; higher scores signify worse symptoms). We will use ANCOVA for the primary analysis, adjusting for baseline GERD symptom severity and visit type assignment using the 8 week follow-up GERD symptom severity as the outcome. Potential moderators that will be assessed in exploratory analyses will include gender (both patient and provider), race, visit length, patient stress, personality type, and perceived connection with/empathy of the provider.

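### Scoring an uncomputable week-8 diary as no change can distort the visit comparison, in a direction that depends on why scores are missing; 9.5.1 names neither a primary population nor a missing-data method

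*Combined protocol and SAP*

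**What the plan says.** Section 5.4 averages whatever days were completed when a diary comes back incomplete, and then adds: "If there is insufficient data to make this calculation, we will assume that symptoms are unchanged from baseline". It does not say how many days are too few. The six-of-seven-day standard in that section defines adherence, not a usable score.

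Section 9.5.1 gives the model: "We will use ANCOVA for the primary analysis, adjusting for baseline GERD symptom severity and visit type assignment", with the week-8 score as outcome. It names no population and does not mention missing scores. Section 9.3 defines two sets without saying which one decides. For the first it says: "The intent to treat analysis will include all randomized subjects who received a study visit intervention". The second, the per protocol set, is limited to people who had the visit and also filled in the week-8 questionnaires; the diary is not part of its definition.

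The documents foresee several routes to a missing score. Section 9.4 sets a review trigger at 20% dropout from adverse effects. After severe symptoms, section 7 says that "the subject may need to initiate additional medication and possibly be removed from the study". Under section 8, subjects who decline study procedures "will be terminated from the study without further follow-up". For those who only stop the medication, section 8 says that "the subject will continue to be followed for the duration of their initially planned participation".

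**The concern.** The rule has two readings. On the broad reading it covers every subject without a usable week-8 diary. The intent-to-treat set requires no week-8 data, so the imputed values would most naturally enter the primary ANCOVA. On the narrow reading it covers only diaries that were returned but are unusable, because the preceding sentence is about returned, incomplete diaries. A subject who returns nothing is then in the intent-to-treat set with no stated handling. Either way 9.5.1 is incomplete.

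On the broad reading, no change is not a neutral value. Section 9.1 hypothesises that expanded-visit subjects "will have a greater improvement in their GERD symptoms after 8 weeks of treatment" than standard-visit subjects, and all subjects receive active medication. Setting the change to zero removes both the shared improvement and the visit effect for each imputed subject. The three routes to loss also call for different assumptions: after a severe flare, no change may even be too favourable.

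The per protocol set is only a partial check. It is defined by the follow-up questionnaires, which section 10.1 allows to be completed from an emailed link. A questionnaire completer with no usable diary stays in that set with an imputed value.

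**Working it through.** **The plan's own figure.** Section 9.2 has 30 per arm, two-sided alpha 0.05 and 80% power. A two-sample t-test (noncentral t, 58 df) gives detectable differences of 1.103, 1.471 and 1.839 for SD 1.5, 2.0 and 2.5. The table's 1.10, 1.47 and 1.84 reproduce.

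**Equal loss unrelated to outcome.** Let Y = a + bX − dG + e, with X the baseline score, G = 1 for the expanded visit and d the true benefit. If Y is replaced by X with probability m, then

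E[Y*|X,G] = (1−m)(a + bX − dG) + mX,

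so the ANCOVA estimates (1−m)d. With d = 1.10: 1.10 × 0.90 = 0.99 and 1.10 × 0.80 = 0.88.

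**Power.** This was simulated, because imputed zeros also change the variance. Assumptions not in the documents: baseline normal (mean 5.5, SD 1.8) truncated to 3–12; slope of change on baseline −0.3; standard-arm improvement 1 to 2 points; enough subjects randomised to leave about 60 observed scores, in line with section 3's plan to enrol until 60 complete. Effect 1.10 and SD 1.5 come from 9.2.

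| Loss per arm | Estimate, rule applied | Power, rule applied | Power, observed scores |
|---|---|---|---|
| 5% | 1.04 | 73–77% | 78–80% |
| 10% | 0.99 | 66–74% | about 79% |
| 20% | 0.88 | 57–69% | about 79% |

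Section 9.2 expects the SD to exceed 1.5. At SD 2.0–2.5, with effects 1.47 and 1.84, power under the rule is 70–76% at 10% loss and 66–75% at 20%. With equal loss and no true effect, type I error stays at 4.4–5.3%.

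**Unequal loss unrelated to outcome, no true effect.** The false difference is the gap in loss times the mean improvement, in favour of the arm with less loss. For 10% v 20% and improvement 2 it is 0.10 × 2 = 0.20. The variance of change in an arm with loss m is (1−m) × 2.25 + m(1−m) × 4, that is 2.385 and 2.44. With 35 per arm, SE = √(4.825/35) = 0.371, and two-sided type I error is 8.4% (simulated 9.0%). At improvement 1 and 1.5 the simulated values are 6.1% and 7.0%. Direction matters: if the expanded arm loses more, the false difference goes against it, and only about 0.7% of null trials significantly favour it.

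**Loss that follows worse outcomes, true effect present.** Here the log-odds of loss rise by 1 per SD of worse change, with the same mechanism in both arms, 34 randomised per arm, effect 1.10 and SD 1.5.

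| Loss, standard / expanded | Rule: estimate, power | Observed scores: estimate, power |
|---|---|---|
| 10% / about 5.5% | 1.05–1.08, 80–83% | 1.04–1.05, 79–80% |
| 20% / about 12% | 0.99–1.08, 75–78% | 0.99–1.01, 73% |

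**Loss that follows worse outcomes, no true effect, 10% standard v 20% expanded.** The rule is biased by −0.02 to −0.11, against the expanded visit (type I error 4.9–6.0%). Observed scores are biased by +0.11 to +0.12, towards it (5.8–6.2%).

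**Per protocol set.** If 0–25% of the missing diaries belong to questionnaire completers, the estimate is 1.07–1.10 at 10% loss and 1.03–1.10 at 20%. Most of the shrinkage goes, but not necessarily all of it.

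**The case against.** The strongest reply is that the shrinkage needs loss unrelated to outcome, while adverse-effect dropout and removal after severe symptoms may well be related to it. In that case the rule is not worse than an observed-score analysis, and the observed-score analysis can lean towards the hypothesised benefit. This stands. A reader might infer that the rule always weakens the trial, or that observed scores are always better. The documents support neither, because they do not settle why scores will be missing.

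It is also fair that the rule may be narrow. It follows a sentence on returned diaries, and any completed day appears to allow an average. On that reading most of the figures above fall away, and the gap is unreturned diaries.

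Exposure may be small. Subjects who stop medication are followed, two reminder calls are planned (6.2.6), and Visit 2 can be remote. At 5% loss the power cost is only 1–6 points. Section 9.6 also plans GERD-HRQL, PROMIS GERD and GSRS as corroborating measures, so symptom data from Visit 2 may exist for subjects without a diary.

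Enrolling until 60 complete does not answer the point. It restores the number of observed scores but leaves the lost subjects in the intent-to-treat set.

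**Conclusion.** The point holds in conditional form. If the 5.4 rule fills missing week-8 scores in the intent-to-treat ANCOVA, equal loss unrelated to outcome shrinks the visit effect by exactly the missing fraction in expectation. Unequal loss unrelated to outcome creates a false difference of about 0.1 to 0.2 points at 10% v 20%. With loss related to outcome, the rule may do no harm relative to observed data. The direction of harm therefore depends on a mechanism that the documents leave open, and one fixed value is too little to carry the primary result.

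The shrinkage formula depends on no assumption about SD or improvement. The sizes do: the documents forecast no loss rate, no gap between arms and no mean improvement. The 20% in 9.4 is a review trigger, not a forecast. It would also go too far to say that the plan definitely applies the rule in its primary analysis, since that is inferred from 9.3. Severity is minor to moderate.

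**What to change.** In 5.4, replace the last sentence with:

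> A week-8 average requires at least k completed diary days [sponsor to set k]. Below k, or if no diary is returned, the week-8 score is missing.

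In 9.5.1, keep the planned ANCOVA and add:

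> The primary population is the intent-to-treat set of 9.3. The ANCOVA assumes missing-at-random and uses observed week-8 scores or, preferably, multiple imputation by arm from the baseline and week-1 diaries and, where available, the Visit 2 GERD-HRQL, PROMIS GERD and GSRS scores. Prespecified sensitivity analyses: (a) every missing week-8 score set to its baseline value; (b) a delta (tipping-point) analysis in which imputed scores are worsened separately in each arm, from zero to beyond the point where the imputed mean equals baseline, reporting the deltas that change the conclusion. Missing scores are reported by arm and reason. The per protocol analysis uses no imputed diary values.

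The cost is a few sentences and some programming: no new data and no change to sample size or model. The downside is reliance on missing-at-random. If more subjects with poor outcomes are lost from the expanded arm, the primary analysis can err towards the expanded visit, so both sensitivity analyses are required. The change should be made before unblinding.

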6. STUDY PROCEDURES

6.1 Schedule of Evaluations for Subjects/Patients

Assessment	Telephone Screening: (Day -30 to -7)	Baseline, Enrollment, Randomization: Visit 1 (Day 0)	Post Intervention: Visit 1 (Day 0)	Follow-up: Visit 2 (Day 53 - 60)
Screening Form	X	X		
GERD Daily Symptom Diary Reviewed		X		X
Informed Consent Form		X		
Current Medication List		X		X
Height and weight		X		
Demographics & Health Behaviors		X		
Blood Draw (optional)		X		X
GERD-Health Related Quality of Life Questionnaire (GERD-HRQL)		X		X
Patient Reported Outcomes Measurement Information System (PROMIS) GERD		X		X
Gastrointestinal Symptom Rating Scale (GSRS)		X		X
Perceived Stress Scale-10 (PSS-10)		X		X
Current Stress Question		X	X	X
NEO Five Factor Inventory (NEO-FFI)		X		
Randomization		X		
HRV, respiratory rate, skin temperature, and GSR		X		
Video recording		X		
Study visit		X		
Impressions of the Study Physician			X	
Consultation And Relational Empathy questionnaire (CARE)			X	
HEAL Patient-Provider Connection			X	
Adverse Events				X
Debriefing				X

Schedules of Evaluations for Providers

Assessment	Enrollment	Prior to each subject/patient encounter	After each subject/patient encounter	After the last study visit
Informed Consent Form	X			
Interpersonal Reactivity Index (IRI)	X			
NEO-FFI	X			
Demographics	X			
Intervention Training	X			
PSS-10		X		
Current Stress Question		X		
Fatigue Scale		X		
Physician Satisfaction Questionnaire			X	
Interview at completion of study				X

6.2 Description of Evaluations

6.2.1 Telephone Screening (Day -30 to -7)

A standardized pre-screening form will be used to assess the potential subject's eligibility for the study. See Appendix B.

6.2.2 COVID-19 Screening (Day -1)

A standardized COVID-19 screening form will be used to assess whether the potential subject has symptoms consistent with COVID-19 or exposure to someone recently diagnosed with COVID-19, prior to the scheduled study visit. If the potential subject is experiencing any symptoms or has had a recent exposure, the potential subject will be rescheduled for another time at least 2 weeks later in order to ensure everyone's safety. See Appendix B.3.

6.2.3 Enrollment, Baseline, and Randomization (Visit 1, Day 0)

Potential subjects will be rescreened using the pre-screen form by a study physician. The study physician will also review the baseline symptom dairy to ensure that the individual is symptomatic enough to enroll. If the individual is eligible to participate in the study, they will be given a copy of the consent form to review.

Consenting Procedure and Enrollment

Written informed consent will be obtained by a study team physician (see also section 4.3). The subject will be given adequate time to read the consent form, and any questions the subject has will be answered. The study team physician will confirm that the subject understands that he/she will be connected to physiologic monitors during the visit and that the visit will be video recorded. The physician will also discuss the risks and benefits of taking amitriptyline or omeprazole. The subject will also have the opportunity to choose whether or not to consent to blood draws as part of the study which will involve one blood draw at the first visit and one blood draw at the second visit. The subject will receive a copy of the consent form and the original signed copy will be kept in a study binder. If the subject agrees to participate and signs the informed consent form, they will be considered "enrolled".

Study providers will be consented by the study PI, following a similar process, using a different written informed consent form.

Baseline Assessments

Evaluations for study participants/patients (self-administered questionnaires take about 15-25 minutes to complete):

- Current medication List – will be pulled from Epic and verified with the patient by a study team physician
- Height and weight – will be obtained by a study team member.
- Demographics and health behaviors – will access things such as age, gender, race/ethnicity, smoking status, alcohol & caffeine use (see Appendix D)
- Blood draw (optional) – 10 mL of blood will be obtained by a trained study staff member or phlebotomist. Blood will be processed to obtain RNA, DNA, and plasma then frozen at -80°C for later omics analyses.
- Baseline Symptom Diary – 7-day diary indicating the frequency and severity of 9 different GERD and dyspepsia-related symptoms on a 5-point scale as well as any medications, supplements, or other products used to help manage symptoms. The first 3 symptoms (daytime heartburn, nighttime heartburn, and acid reflux) will be used to assess severity of GERD symptoms.
- GERD-HRQL – a validated 11 item scale for assessing the impact of GERD symptoms on health-related quality of life⁷³.
- NIH PROMIS GERD scale – a validated 13 item instrument assessing frequency and severity of GERD symptoms over a 7-day recall period²⁶.
- GSRS: The Gastrointestinal Symptom Rating Scale is a validated 15 item instrument for measuring the severity of gastrointestinal symptoms⁷⁴. It contains 5 subscales: abdominal pain, reflux syndrome, diarrhea syndrome, indigestion syndrome, and constipation syndrome.
- Current Stress Question – 1 item self-report measure of current stress level on a scale of 0 (no stress) to 10 (extreme stress)
- Perceived Stress Scale (PSS) – a widely used 10 item measure of perceived stress that has been shown to correlate with a variety of different health outcomes⁷⁵. We have adapted the originally validated measure to ask about stress over the past week (7 days), rather than the past month, to better fit the timeframe of the study. We have used this timeframe in other studies.
- NEO Five Factor Inventory (NEO-FFI) – a validated 60 item instrument that measured five major dimensions of personality: extraversion, neuroticism, agreeableness, conscientiousness, and openness to experience⁷⁶. Some dimensions have been associated with response to enhanced patient-provider interactions in others' studies⁷⁷.
- Physiologic Measures and Video Recording: During the intervention we will measure HRV, respiratory rate, skin temperature, and GSR in both study patients and study providers. The study visit will also be video recorded. During the COVID-19 pandemic, in order to allow us to collect physiologic and nonverbal behavior data (e.g., smiles) with the patient and physician unmasked, while also complying with institutional and state public health guidelines, the patient and doctor will sit in separate but adjacent, exam rooms with the door closed and use a video telehealth platform (e.g., Zoom, Cisco Meeting) to communicate. We will use the recording function to capture video data.

Evaluations for study providers:

- Interpersonal Reactivity Index (IRI) – a validated 28 item self-assessment of cognitive and affective components of empathy⁷⁸.
- NEO Five Factor Inventory (NEO-FFI) – a validated 60 item instrument that measures five major dimensions of personality: extraversion, neuroticism, agreeableness, conscientiousness, and openness to experience [73]. Some dimensions have been associated with response to enhanced patient-provider interactions in others' studies⁷⁷.
- Demographics and practice – will assess things such as age, gender, race/ethnicity, and clinical experience (see Appendix D).
- Current Stress Question – 1 item self-report measure of current stress level on a scale of 0 (no stress) to 10 (extreme stress). Study providers will complete this question immediately prior to each study subject visit.
- Perceived Stress Scale (PSS) – a widely used 10 item measure of perceived stress that has been shown to correlate with a variety of different health outcomes⁷⁵. Study providers will complete this questionnaire immediately prior to each study subject visit.
- Fatigue Scale – 1 item self-report measure of the current fatigue level on a scale of 0 (no fatigue) to 10 (extreme fatigue). Study providers will complete this question immediately prior to each study subject visit.
- Physician Satisfaction Questionnaire (PSQ) – 20 item self-report measure assessing physician satisfaction with the patient visit. This measure includes a global satisfaction question and 19 items assessing 4 other domains: satisfaction with the patient-physician relationship, with the data collection process, with the appropriateness of the use of time, and with the absence of excessive demands on the part of the patient. Study providers will complete this questionnaire immediately after each study visit⁷⁹.

Randomization

Subjects will be randomized on the day of their baseline visit (Visit 1) to receive either the standard or expanded visit with the specific provider that they are scheduled to see that day. We will stratify randomization by provider so that each provider does the same proportion of standard and expanded visits. Randomization will occur during or immediately after subjects have completed their baseline questionnaires, immediately prior to the study visit.

